## Procedures performed to monitor participants for safety

N/A

### **Biospecimens**

N/A

### **Drugs and devices**

The Leva Pelvic Health System and associated smartphone application will be utilized in this research as the administered treatment to assess the primary endpoint.

### Data will be collected during the study

- In office examination at first visit and 16 weeks
  - Limited Physical Examination will include the collection of the following data:
    - Vitals (height, weight, pulse, blood pressure)
    - POP-Q
    - Brink Scale Score
- Leva smartphone application surveys administered at 0,4,8,12,16 weeks
  - $\circ$  UDI-6
  - o CRADI-8
- Administration of electronic surveys at 0, 16 weeks and 24 weeks via emailed weblink.
  - o St Mark's (Vaizey)
  - o Bristol Stool Scale
  - o FIQoL
  - PISQ-IR
  - o PGI-I
  - o Patient satisfaction
  - o Estimated percent improvement
  - mHealth App Usability Questionnaire (MAUQ)
  - o PFDI-20
- *Questionnaires, structured interviews, or other assessments.* Attached
- Source records that will be used to collect data about participants. UW Health HealthLink Records (study team will directly access)

Long-term follow-up data

- Administration of surveys at 6 months by mail or email
  - o Bristol Stool Scale
  - St Mark's (Vaizey)
  - o FIQoL
  - o PISQ-IR
  - o PGI-I
  - Patient satisfaction
  - Estimated percent improvement
  - mHealth App Usability Questionnaire (MAUQ)
  - o PFDI-20
- To evaluate self-continuation of pelvic floor muscle exercises, at 16 and 24 weeks.
- Long-term follow up data will be collected by adminstration of electronic surveys completed at 1 year and 2 years from enrollment date:
  - Bristol Stool Scale
  - St Mark's (Vaizey)
  - o FIQoL
  - PISQ-IR
  - o PGI-I
  - Patient satisfaction
  - Estimated percent improvement
  - o PFDI-20

### Regulatory status of all drugs and devices used in the study

The Leva Pelvic Health System is FDA cleared and commercially available.

## 14.0 Comparison of usual care and study procedures

### Describe the current alternatives to participation in this research study.

If a participant chooses not to participate in this study, they can continue to receive standard clinical care, which is initiated with conservative management.

### Describe standard practice or standard of care for this participant population

Standard clinical care is initiated with conservative management.

Typically, patients who are presenting for management of chronic fecal incontinence will initially be managed with medical therapy (diet supplementation with bulking agents and / or anti-diarrheal agents) to improve stool consistency.

Subsequent therapy may include biofeedback, followed by advanced therapy options, like surgery.

Typical follow up is 3-4 months.

### List any research procedures that overlap with standard practice

The research procedure utilizes Leva Pelvic Health System (a digital therapeutic system that includes an intra-vaginal device that pairs with a smartphone application) to provide real-time visual feedback about pelvic floor muscle performance during use.

While the primary end point of the study is to assess non-inferiority of use of Leva for 8 weeks to 16 weeks, an overlap to standard clinical treatment is the smartphone application educational material. The Leva application provides educational and motivational content in the form of 'daily tasks.' At each training session, participants will have the opportunity to watch a brief educational video or read a short informative message or article presented to them that describes their health condition, helpful behavioral modifications (e.g., toileting posture, breathing exercises, dietary changes or supplementation with bulking agents or anti-diarrheal agents), or words of support or motivation. Engagement with these tasks is optional (PFMT can be completed without completing the task), but participants will be encouraged to access this content to ensure they are provided standard clinical education regarding chronic fecal incontinence.

### Describe whether research participation would affect standard clinical care

This study is not anticipated to affect standard clinical care.

While participants will not meet with a clinician for the usual treatment of fecal incontinence, they will receive standard conservative management education through the Leva smartphone application engagement, as well as the self-guided treatment through Leva.

## **15.0 Withdrawal of Participants**

## Circumstances under which participants will be withdrawn from the research without their consent.

Removal of Participants from Study:

- Participants are free to withdraw from the study at any time, for any reason.

Participants will be asked for a reason for withdrawal. If due to any adverse event, they will be managed as appropriate and followed until resolution. Participants will be asked if collected data can be utilized or completely withdrawn. Participants will be asked if they can be contacted in the future by the study team.

Participants will be able to keep or dispose their device.

Participants may be withdrawn from the study for the following reasons:

- Participant is unable to use the Leva Pelvic Health System
- Participant experiences a severe adverse effect
- Participant does not follow the study instructions or return for follow up visits
- Participant needs a treatment not allowed while participating in the study
- If the study is stopped by researchers

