## **11.0 Study Intervention**

### **Description:**

The Leva Pelvic Health System is a commercially available digital therapeutic system that is FDA-cleared for the treatment of chronic fecal incontinence (symptoms >/= 3 months) in women, for stress, urgency, and mixed urinary incontinence in women, and for pelvic floor muscle strengthening in women. The system includes an intra-vaginal device that pairs with a smartphone application to provide real-time visual feedback about pelvic floor muscle performance during use. The training protocol embedded in the device/app includes 5 cycles of 15-second contraction followed by a 15-second rest period. This 2.5-minute training protocol is completed twice daily. Participants will be instructed to follow this training regimen with the Leva Pelvic Health System for either 8 or 16 weeks. The device will be shut off remotely by Leva at the end of the allocated 8- or 16-week study period and participants will be able to keep or dispose of the device.

In addition to guiding PFMT, the Leva app also provides educational and motivational content in the form of 'daily tasks.' At each training session, participants will have the opportunity to watch a brief educational video or read a short informative message or article presented to them that describes their health condition, helpful behavioral modifications (e.g., toileting posture, breathing exercises, dietary changes), or words of support or motivation. While engagement with these tasks is optional (PFMT can be completed without completing the task), participants will be encouraged to access this content.

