### Procedures for orderly termination.

Should study participants require termination from research due to any of the above listed reasons. They will be notified and instructed that they can keep or dispose of the device.

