## Describe procedures that will be followed when participants withdraw from the research

No future/continued data will be collected from participants who withdraw from research. The device will be kept or disposed of by the study participants.

If withdrawal is due to any adverse event, they will be managed as appropriate and followed until resolution.

Participants will be asked if they can be contacted in the future by the study team.

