### LOST TO FOLLOW UP

The study team will mail a Certified Letter (Must be signed for) to study participants who they have not be able to reach at one year after enrollment. The letter will be sent to the most current address on file. If the study team does not receive a response, the study team will designate them as lost to follow up and no longer attempt to reach the subject. The letter is uploaded to the Supplemental Information section.

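### Participants can be removed for not following instructions or missing visits, and the plan does not say that their emailed outcome surveys continue

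*Combined protocol and SAP*

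**What the plan says.** Section 15.0, under its heading on withdrawal without consent, lists reasons for which participants may be withdrawn. One is "Participant does not follow the study instructions or return for follow up visits". The list is permissive. It gives no adherence threshold and does not define the instructions.

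The paragraph on orderly termination begins "Should study participants require termination from research due to any of the above listed reasons" and goes on to notification and what happens to the device. It does not mention data. The next paragraph says "No future/continued data will be collected from participants who withdraw from research", keeping only follow-up of adverse events to resolution.

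Section 13.0 specifies "Administration of electronic surveys at 0, 16 weeks and 24 weeks via emailed weblink", and St Mark's/Vaizey heads that list. Clinic attendance is separate: "In office examination at first visit and 16 weeks". Week 16 is therefore the only follow-up visit.

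Section 11.0 sets the regimen: "Participants will be instructed to follow this training regimen with the Leva Pelvic Health System for either 8 or 16 weeks", with two sessions a day. It adds: "The device will be shut off remotely by Leva at the end of the allocated 8- or 16-week study period".

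**The concern.** Stopping or neglecting the device is not the same as leaving the study, but section 15.0 treats them together. A participant who trains poorly, or does not come to clinic, can still answer an emailed questionnaire. If the team removes her and the surveys stop, the trial loses a primary score that it could have had.

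The reason for the loss arises after randomisation and is tied to the randomised factor. The 16-week arm has twice as long a regimen to follow, and between weeks 8 and 16 it is the only arm with a device regimen at all. Exposure to the removal rule may therefore differ by arm, and a comparison of those retained is no longer fully protected by randomisation.

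The bias could go either way. If removed 16-week participants would have done worse than those kept, that arm looks better than it is and non-inferiority is harder to show. If they stopped training because they had improved, the opposite holds.

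A secondary objective is also exposed. The plan will relate adherence to symptom change, and removing poor adherers takes out the low end of that relationship.

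**Working it through.** **Which scores are at risk**

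- Removal for not following instructions before week 16 can lose both the week-16 and the week-24 score.
- Removal for a missed week-16 visit mainly threatens week 24, plus any week-16 survey not yet submitted.
- No other text restores collection. The lost-to-follow-up paragraph covers "study participants who they have not be able to reach at one year after enrollment", not people who were removed. Section 22.0 lets participants with complaints stop the device but is silent on surveys. The section 20.0 paragraph on analysis populations names no analysis set.

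**Exposure to the rule by arm** (section 11.0, training every day)

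- 8-week arm: 2 × 7 × 8 = 112 sessions.
- 16-week arm: 2 × 7 × 16 = 224 sessions.

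**The plan's own sample size** (section 20.0: SD 4.37, change −3, margin 1, α 0.05, power 80%, attrition 20%, 19 per arm)

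- The figure of 19 is reproduced with one-sided 0.05 and a distance of 1 + 3 = 4: n = 2 × 4.37² × (1.645 + 0.842)² / 4² = 14.8, so 15; 15 / 0.8 = 18.75, so 19.
- This enters the change from baseline as if it were a difference between arms. That is a separate problem and does not affect this point. Only the 19 enrolled and about 15 retained are used below (0.8 × 19 = 15.2).

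**Standard error of the difference**

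- 15 per arm: 4.37 × √(2/15) = 1.60.
- 19 per arm: 4.37 × √(2/19) = 1.42.
- Reduction if every lost score were recovered: 1 − √(15/19) = 11%. This is an upper limit, because not all attrition comes from this rule.

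**Bias from unbalanced losses**

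Suppose k extra participants are lost from one arm of 19, and their mean change would have differed by d points from those kept. The mean of those kept then differs from the full-arm mean by k × d / 19. Both k and d are assumptions. The 3-point value equals the plan's expected mean change; the true gap could be smaller or larger.

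| Extra losses k | Gap d | Shift (points) | Share of 1-point margin | Shift / SE of 1.60 |
|---|---|---|---|---|
| 1 | 1 | 1/19 = 0.05 | 5% | 0.03 |
| 1 | 3 | 3/19 = 0.16 | 16% | 0.10 |
| 2 | 1 | 2/19 = 0.11 | 11% | 0.07 |
| 2 | 3 | 6/19 = 0.32 | 32% | 0.20 |

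As a more extreme case, if 20% of one arm were removed and none of the other, the shift would be 0.20 × 3 = 0.6 point for a 3-point gap and 0.20 × 5 = 1.0 point, the whole margin, for a 5-point gap. If losses and gaps balance across arms, the bias is zero.

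**Timing** (section 12.0: start September 2023, about one year of enrolment)

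- Last enrolment taken as 30 September 2024: + 16 weeks = 20 January 2025; + 24 weeks = 17 March 2025.
- Latest version date in the revision history: 23 January 2025.

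**The case against.** The strongest reply is that this is an ambiguity in a discretionary clause. The rule says participants may be withdrawn, and nothing shows that routine use is intended. The trial is called pragmatic and has an objective relating adherence to outcome, which suggests that poor adherers are meant to be kept and scored. The sentence stopping data collection speaks of participants who withdraw, which could mean only those who leave by choice. The consent form, not available here, may address the matter. The 8-week arm may also have instructions after week 8, since section 13.0 schedules app surveys at weeks 12 and 16 without separating the arms. The missing-data paragraph in section 20.0 already promises recorded reasons and sensitivity analyses. On the planned dates most week-16 scores have already been collected or lost.

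Part of this stands. The rule may rarely be used, its reach to removed participants is inferred, the likely effect is modest, and the remedy may come too late for many primary scores.

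The rest does not answer the point. The three withdrawal paragraphs form one section whose heading calls removed people withdrawn, so the natural reading is that their data collection stops. The adherence objective strengthens the concern, because it needs scores that the rule allows to be discarded. The missing-data paragraph starts from missing at random and cannot replace scores never collected. Recorded adherence can enter a model, but removal for a missed visit or for needing a disallowed treatment need not be explained by adherence.

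**Conclusion.** The concern holds. Followed as written, section 15.0 can discard primary scores that could have been obtained, for reasons that arise after randomisation and may differ between arms. This rests on reading the stop on data collection as covering participants removed by the team, which is natural but not explicit.

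Under the assumed gaps, one or two extra losses in one arm matter little against a standard error of 1.60. A clear imbalance with a large gap could use up much of the 1-point margin. Neither the size nor the direction can be settled from the documents. The change should be made because it is cheap and removes an avoidable source of bias; the point does not by itself invalidate the trial.

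**What to change.** - In section 15.0, separate stopping the device from leaving the study, and state that non-adherence or a missed visit does not end outcome collection.
- In the paragraph on orderly termination, say what happens to data after removal by the team.
- Keep emailing the 16- and 24-week surveys to everyone randomised, and the 1- and 2-year surveys to those who consented to them, unless the participant withdraws consent to follow-up.
- In section 20.0, make the primary comparison in all randomised participants as assigned. The missing-data model can include arm, baseline score and, optionally, app-recorded adherence over the assigned period.

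No change is proposed to when a participant stops using the device.

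The cost is protocol and consent wording, a few more emailed surveys and modest analysis work. Actual enrolment status is not stated. Where the week-16 window has passed, only the later surveys and the analysis change apply, and the analysis change should be fixed before the data are examined.

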### Procedures for orderly termination.

Should study participants require termination from research due to any of the above listed reasons. They will be notified and instructed that they can keep or dispose of the device.

## Describe procedures that will be followed when participants withdraw from the research

No future/continued data will be collected from participants who withdraw from research. The device will be kept or disposed of by the study participants.

If withdrawal is due to any adverse event, they will be managed as appropriate and followed until resolution.

Participants will be asked if they can be contacted in the future by the study team.

### LOST TO FOLLOW UP

The study team will mail a Certified Letter (Must be signed for) to study participants who they have not be able to reach at one year after enrollment. The letter will be sent to the most current address on file. If the study team does not receive a response, the study team will designate them as lost to follow up and no longer attempt to reach the subject. The letter is uploaded to the Supplemental Information section.

## **16.0 Data Management and Confidentiality**

### Describe any procedures that will be used for quality control of collected data.

All Leva user's complete device registration and provide informed consent for personal and device-related data to be cloud-captured and stored in a HIPAA-compliant manner (Supplement 1). This information includes user demographics, presence and degree of bother of incontinence symptoms, and adherence (i.e., the number of training sessions completed in a given timeframe). For this study, all user data will be coded prior to analysis of user characteristics/variables and treatment outcomes.

The app will be undergoing a UW-Madison cybersecurity risk assessment, requested through OneTrust. Any recommendations that come out of the cybersecurity risk assessment would be implemented once the review is completed.

### Describe the steps the researchers will take to secure the data

- [x] Data will be coded, and the "key" linking identities to codes will be kept separately from the data.
- [x] Only those listed as key personnel will have access to the "key."

[] Other: \_\_\_\_\_\_

Patient contact information will be stored separately from the study ID number, and all sensitive data collected will only be identified with study ID numbers. The electronic file linking study ID number and patient's identity will be stored in a password-protected data file on a secure shared drive accessible only to the principal investigator, research assistant, and clinical research coordinators who communicate with the participants.

Data will be collected and stored in REDCap (https://redcap.ictr.wisc.edu).

All researchers / investigators will ensure data management methods are HIPAA compliant.

All personnel with access to individual patient data will be trained in the maintenance of confidentiality of Protected Health Information as required by the Health Insurance Portability and Accountability Act (HIPAA) of 1996.

The University of Wisconsin requires all researchers working with human subjects to take online training courses provided by the Collaborative Institutional Training Initiative (CITI). The IRB proposal form will be submitted understanding that the Principal Investigator has completed the required training.

### Describe how and where data will be stored and maintained

- **[x]** Research Electronic Data Capture (REDCap) ICTR
- **[x]** Data will not be stored or accessed on portable devices.
- **[x]** Portable devices will be used to access secure web-based data collection sites such as ICTR's REDCap. No data will be stored locally on the device.
- **[x]** Screening and enrollment logs will be stored on the UW-Madison Obstetrics and Gynecology secure department server.

### Management of Identifiers:

**[x]** Any identifiers will be destroyed at study closure or at the time of publication.

### Describe any planned sharing of data outside the study team / institution

Coded Leva smartphone application usage data will be reported to study investigators and transferred to REDCap prior to statistical analyses.

Note that The Leva Pelvic Health System is an FDA-cleared and commercially available device for which users complete device registration and provide informed consent for personal and device-related data to be cloud-captured and stored in a HIPAA-compliant manner (Supplement 1). For the purposes of this study, any data shared between the University of Wisconsin researchers and Axena Health (The Leva Pelvic Health System) will be coded prior to analysis of user characteristics and treatment outcomes.

To ensure appropriate confidentiality protections, PHI will not be shared from study researchers to the Leva team.

### Whether data will have all identifiers removed prior to sharing.

Patient contact information will be stored separately from the study ID number, and all sensitive data collected will only be identified with study ID numbers. The electronic file linking study ID number and patient's identity will be stored in a password-protected data file on a secure shared drive accessible only to the principal investigator and research assistant.

### How data will be transmitted or transported.

Coded Leva smartphone application usage data will be reported to experimenters and transferred to REDCap prior to statistical analyses.

### Describe limitations on the sharing of data, if any.

Participant data will be coded and linked to participant identifiers. There are no limitations on the sharing of data.

## **17.0** Provisions to Protect the Privacy Interests of Participants

### Describe the steps that will be taken to protect participants' privacy interests.

- [x] Procedures will be performed in a private area where others cannot see the procedures being performed or overhear the conversation between subjects and researchers.
- [x] All members of the study team are up to date on their institutional HIPAA training.
- **[x]** The study is not collecting information that could pose legal or reputational risks to participants.

### Sensitive information

This study will collect information on fecal incontinence, bowel movement consistency, pelvic floor and pelvic floor musculature, satisfaction, quality of life, and sexual function. Collection of sensitive information about participants is limited to the amount necessary to achieve the aims of the research. Collection of this information from participants is justified as fecal incontinence and pelvic health are interrelated, and it is important to assess the impact of treatment on these other listed aspects of health.

### Steps you will take to make the participants feel at ease with the research

Establishing rapport with participants in order to guarantee the validity and integrity of the study. Ensure participant understanding that research investigators and team will always act in accordance with ethical guidelines and solutions in order to protect the participants from risks and maintain their privacy by establishing confidentiality.

